Appendix III Protocol Amendment 1.0 and List of Changes

[figure not shown]
Appendix III Frotocol Amendment 1.0 and List of Changes				
CCI				
•				
-				
			_ 10	4/131

[figure not shown]

[figure not shown]

[figure not shown]
107/131

[figure not shown]

108/131

[figure not shown]

111/131

[figure not shown]
112/131

China First-line Head and Neck Trial (CHANGE2)

113/131

Document No. Object No.

China First-line Head and Neck Trial (CHANGE2)

Cetuximab EMR062202-060

China First-line Head and Neck Trial (CHANGE2)

[figure not shown]

[figure not shown]
China First-line Head and Neck Trial (CHANGE2)

CCI

[figure not shown]
CCI

[figure not shown]

[figure not shown]

[figure not shown]

[figure not shown]

[figure not shown]

[figure not shown]

[figure not shown]

Document No. Object No.

[figure not shown]

[figure not shown]

[figure not shown]

Document No. Object No.

### 3 List of Abbreviations and Definition of Terms

|       |  |
|-------|--|
| AE    | Adverse Event                                  |
| AUC   | Area under Curve                               |
| BOR   | Best overall response                          |
| BP    | Blood Pressure                                 |
| BSA   | Body surface area                              |
| CDISC | Clinical Data Interchange Standards Consortium |
| CI    | Confidence interval                            |
| CR    | Complete response                              |
| CT    | Computed tomography                            |
| CTR   | Clinical Trial Report                          |
| CTX   | Chemotherapy                                   |
| DBP   | Diastolic Blood Pressure                       |
| DCR   | Disease control rate                           |
| DI    | Dose Intensity                                 |
| DOR   | Duration of Response                           |
| EAIR  | Exposure Adjusted Incidence Rate               |
| ECG   | Electrocardiogram                              |
| ECOG  | Eastern Cooperative Oncology Group             |
| eCRF  | Electronic Case Report Form                    |
| EOEA  | End of efficacy assessment                     |
| EoS   | End of Study                                   |
| 5-FU  | 5-fluorouracil                                 |
| GFR   | Glomerular Filtration Rate                     |
| HBV   | Hepatitis B Virus                              |
| HCV   | Hepatitis C Virus                              |
| HIV   | Human Immunodeficiency Virus                   |
| HPV   | Human Papilloma Virus                          |
| ICH   | International Conference of Harmonization      |
| Inv   | Investigator                                   |
| IRC   | Independent Review Committee                   |

|           |  |
|-----------|--|
| IRR       | Infusion-related reaction  |
| ITT       | Intention-to-Treat   |
| IWRS      | Interactive Web Response System  |
| LVEF      | Left Ventricular Ejection Fraction   |
| MedDRA    | Medical Dictionary for Regulatory Activities                               |
| MN        | Miettinen & Nurminen   |
| MRI       | Magnetic resonance imaging   |
| NCI-CTCAE | National Cancer Institute – Common Terminology Criteria for Adverse Events |
| NE        | Not evaluable  |
| OS        | Overall Survival   |
| PD        | Progressive Disease  |
| PFS       | Progression-Free Survival  |
| PP        | Per Protocol   |
| PR        | Partial response   |
| PT        | Preferred Term   |
| RECIST    | Response Evaluation Criteria in Solid Tumors                               |
| RDI       | Relative Dose Intensity  |
| SAE       | Serious Adverse Event  |
| SAF       | Safety Analysis Set  |
| SAP       | Statistical Analysis Plan  |
| SBP       | Systolic Blood Pressure  |
| SCCHN     | Squamous cell carcinoma of the head and neck                               |
| SCR       | Screening  |
| SD        | Stable Disease   |
| Sd        | Standard Deviation   |
| SDTM      | Study Data Tabulation Model  |
| SOC       | System Organ Class   |
| TCM       | Traditional Chinese Medicine   |
| TEAE      | Treatment Emergent Adverse Event   |
| TLF       | Tables, Listings, and Figures  |
| TNM       | Tumor-Nodes-Metastases   |
| WHO-DD    | WHO Drug Dictionary  |

## 4 Modification History

| Unique Identifier for SAP Version | Date of SAP Version | Author            | Changes from the Previous Version   |
|-----------------------------------|---------------------|-------------------|---|
| Final 1.0                         | 10NOV2016           | [name]    | First version   |
| Version 2.0                       | 19FEB2018           | [name]        | Add 3-tier approach
Add analysis for clintrial.gov
Add Chinese origin/citizenship
Remove lab parameters analysis over each visit
Remove repeated baseline TLFs on each subgroup
Remove hypothesis test according to protocol
Remove each chemotherapy drug related AE and replace it with chemotherapy related AEs
Remove subgroup Type of primary tumor; HPV
Update protocol deviation list and the definition of Per Protocol analysis set
Update the definition of PFS according to the most recent draft protocol
Update the shift category for vital signs |
|                                   | 16APR2018           | [name] | Update the list of analyses of Adverse Events
Update actual dose definition for Carboplatin
Add definitions of the CTCAE v4.03 Grades for Laboratory Parameters
Clarify Concomitant Medication and Procedures and delete Prior Non Anti-Cancer Medications section
Add Line of treatment to Anti-cancer treatment after discontinuation
Add RDI for carboplatin
Update Protocol Deviations list
Add a new sensitivity analysis to the primary endpoint
Several updates of wording for consistency with protocol amendment and clarification                           |

## 5 Purpose of the Statistical Analysis Plan

The purpose of this SAP is to document technical and detailed specifications for the main and final analyses of data collected for protocol EMR062202-060.

Results of the analyses described in this SAP will be included in the Clinical Trial Report (CTR) and in the CTR addendum (for results based on all data collected until OS cut off - e.g., at least 180 deaths [e.g., 75% of randomized subjects] have been reported, or up to 12 months after the last subject is randomized, whichever is earlier). Any post-hoc, or unplanned analyses performed to provide results for inclusion in the CTR but not identified in this prospective SAP will be clearly identified in the CTR.

The SAP is based upon Section 8 (Statistics) of the trial protocol and protocol amendments (last version dated 26 February 2018) and is prepared in compliance with International Conference on Harmonization (ICH) E9.

## 6 Summary of Clinical Trial Features

### Objectives:

Primary objective: The primary objective of this trial is to evaluate whether progression-free survival (PFS) time, as assessed by an Independent Review Committee (IRC), in subjects receiving cetuximab in combination with cisplatin plus 5-fluorouracil (5-FU) is longer than that in subjects receiving cisplatin plus 5-FU alone in the first-line treatment of recurrent and/or metastatic squamous cell carcinoma of the head and neck (SCCHN).

Secondary objectives: The secondary objectives are to compare the 2 treatment arms in the following:

- PFS time, as assessed by the Investigator
- Overall survival (OS) time
- Best overall response (BOR) rate
- Disease control rate (DCR)
- Duration of response
- Safety

### Methodology:

This is an open-label, randomized, parallel-group trial. At the end of a 28-day screening period, all eligible subjects will be randomly assigned into treatment Arm A or B in a 2:1 ratio. Subjects in Arm A will receive a maximum of 6 cycles of chemotherapy (cisplatin plus 5-FU) and cetuximab weekly in the absence of progressive disease (PD), as assessed by the Investigator, and unacceptable toxicity. After 6 cycles of treatment, subjects who derive clinical benefit will continue treatment with cetuximab as monotherapy until either PD or unacceptable toxicity. Subjects in Arm B will receive the same chemotherapy regimen as Arm A alone for a maximum of 6 cycles in the absence of PD and unacceptable toxicity.

Tumor assessment will be performed according to Response Evaluation Criteria in Solid Tumors (RECIST) version 1.1. The baseline tumor assessment is to be performed during the screening period within 28 days before the start of trial treatment. Computed tomography (CT) or magnetic resonance imaging (MRI) with contrast enhancement is recommended for tumor assessment. Subsequent tumor response evaluations will be assessed every 6 weeks ( $\pm$  3 days) starting from the randomization day until occurrence of PD regardless of any cycle delay. If treatment is discontinued for reasons other than PD, subjects will continue to have tumor assessments until either PD, the start of a new antitumor treatment, death, the termination of the trial, or loss of follow up, whichever comes first. If symptoms are suggestive of PD, subjects will be evaluated by imaging studies thereafter for documentation and confirmation of the tumor responses.

All subjects in Arm A and B will be followed up continuously for safety evaluations according to schedule of assessments in Table 1.1 of the protocol, **Error! Reference source not found.** starting from date of first signature of informed consent. A Safety Follow-up visit will be performed 30 days ( $\pm$  3 days) after the last dose of trial treatment or immediately before starting any new antitumor treatment. During the treatment period, additional safety evaluations will be on a weekly basis (Arm A only) for physical examination, vital signs, documentation of adverse events and concomitant medications, and also at the start of each cycle (for both arms) Eastern Cooperative Oncology Group (ECOG) performance status, electrocardiogram (ECG), hematology, biochemistry and urinalysis. Survival data will be collected every 3 months after the end of efficacy assessment (EOEA) visit until either death, loss of follow up, or the termination of the trial, whichever comes first.

The trial will be terminated when the last subject has discontinued the trial treatment or OS cut-off, whichever is later. After OS cut-off and before the trial termination, only SAEs during treatment and at the EOEA visit will be reported, following the usual reporting procedure. Information collected in the EOEA forms will be limited to data on date of trial treatment completion, date of last treatment, subject status at end of trial, reason for discontinuation, disease progression (yes/no). From alive, but trial-treatment-discontinued subjects, no tumor response data, anti-cancer treatment and survival information will be collected.

**Planned number of subjects:** 240 subjects.

**Primary endpoint:** The primary endpoint is PFS time, as assessed by an IRC.

**Secondary endpoints:** The secondary endpoints include PFS time, as assessed by the Investigator, OS time, BOR rate, DCR, duration of response, and safety.

**Pharmacokinetics:** Not applicable.

**Other assessments:** Not applicable.

**Diagnosis and key inclusion and exclusion criteria:**

Trial population: Subjects who have recurrent and/or metastatic SCCHN excluding nasopharyngeal carcinoma and who have not received chemotherapy for recurrent and/or metastatic SCCHN.

Key inclusion criteria:

- $\geq$ 18 years of age.
- Histologically and/or cytologically confirmed diagnosis of SCCHN.
- Recurrent and/or metastatic SCCHN, not suitable for local-regional treatment. Subjects with recurrent disease only (no metastases) must have received prior radiotherapy (as adjuvant treatment after surgery or as treatment for locally advanced SCCHN) as part of “loco-regional treatment”, and the radiotherapy and the radiotherapy must have been completed more than 6 months before screening imaging.

- Presence of at least 1 measurable lesion according to RECIST version 1.1.
- Signed written informed consent before any trial-related activities are carried out.
- ECOG performance status of 0 or 1.

Key exclusion criteria:

- Prior systemic chemotherapy, except if given as part of multimodal treatment, for locally advanced SCCHN that was completed more than 6 months before randomization.
- Surgery (excluding prior biopsy for diagnosis) or irradiation within 4 weeks before randomization.
- Previous treatment with monoclonal antibody or signal transduction inhibitors targeting epidermal growth factor receptor.
- Nasopharyngeal carcinoma.
- Known central nervous system metastasis and/or leptomeningeal disease.
- Medical or psychological condition that would not permit the subject to complete the trial or sign informed consent.
- Legal incapacity or limited legal capacity.

**Investigational Medicinal Product: dose/mode of administration/ dosing schedule:**

Cetuximab, supplied in ready-to-use 20 mL vials containing 5 mg/mL solution, will be administered on a weekly basis to subjects in Arm A. The initial dose will be 400 mg/m^2 as an intravenous infusion up to a maximum speed of 5 mg/minute. The subsequent weekly dose will be 250 mg/m^2 as an intravenous infusion up to a maximum speed of 10 mg/minute.

**Reference therapy: dose/mode of administration/dosing schedule:**

Subjects in both arms will receive a maximum of 6 cycles of chemotherapy of 75 mg/m^2 cisplatin as intravenous infusion (refer to China package insert) on Day 1 of each 21-day treatment cycle, and then 750 mg/m^2/day of 5-FU as a continuous intravenous infusion over 24 hours ± 6 hours a day from Day 1 to Day 5 of each 21-day treatment cycle.

In the case of cisplatin-related nonhematologic toxicity, cisplatin may be replaced by carboplatin at a dose of target area under the serum concentration time curve of 5 in the subsequent cycles. The decision needs to be made in discussion with the Medical Monitor on a case-by-case basis. Carboplatin will be administered using an intravenous infusion of 15 minutes or longer, and in accordance with the China package insert on Day 1 of each 21-day treatment cycle.

**Planned treatment duration per subject:**

The treatment duration per subject may vary. Subjects will be treated with a maximum of 6 cycles of chemotherapy and/or cetuximab weekly in the absence of PD, as assessed by the Investigator, and unacceptable toxicity. Subjects (in Arm A) who demonstrate at least a tumor

response of stable disease (RECIST version 1.1) after 6 cycles of trial treatment will continue monotherapy with cetuximab until either PD or occurrence of unacceptable toxicity. Subjects who stop treatment before reaching PD will continue to have tumor assessments (CT or MRI) every 6 weeks until either PD, the start of a new antitumor treatment, death, or termination of the trial, or loss of follow up, whichever comes first. Upon occurrence of PD, all trial treatments should be discontinued.

**Statistical methods:**

Sample Size Calculation: CCI

Randomization: Randomization will be performed centrally using an interactive web response system (IWRS). A central stratified permuted block randomization procedure will be used to balance between treatment arms. The stratification factors are ECOG performance status (0 versus 1) and the primary tumor site (oral cavity versus hypopharynx versus others).

Statistical Analyses:

The hazard ratio between the treatment arms in PFS time (based on imaging as assessed by an IRC) will be estimated by Cox's proportional hazards model stratified by randomization strata to assess the stratified hazard ratio. The 95% confidence interval (CI) will also be provided to characterize the variability of the point estimate. In discussion with Chinese Health Authority, this bridging trial would be regarded as positive from regulatory point of view if the point estimation for stratified hazard ratio less than or equal to 0.77. All secondary analyses of the primary variable will be performed to support the results of the primary confirmatory analysis and regarded as purely exploratory.

The time-to-event endpoints will follow standard methodology by employing Kaplan-Meier estimates, Cox's proportional hazard model to estimate stratified hazard ratios and corresponding 95% CI.

The counts and percentages will be summarized for dichotomous data.

The main statistical analysis of data is event driven and is expected to be approximately 22 months after trial initiation (i.e., after the 144 PFS events with respect to the primary endpoint have occurred). The final analysis of OS (OS cut-off date should be at least 180 deaths [e.g., 75% of randomized subjects] have been reported, or up to 12 months after the last subject is randomized, whichever is earlier), will be presented in a clinical trial report addendum. Safety data collected after the OS cut-off will be reported through patient profile. No additional statistical analyses will be conducted.

---

## 7 Sample Size/Randomization

### 7.1 Sample Size

CCI [REDACTED]

CCI [REDACTED]

[REDACTED]

[REDACTED]

[REDACTED]

[REDACTED]

CCI [REDACTED]

CCI [REDACTED]

[REDACTED]

### 7.2 Randomization

Subjects will be randomized to one of the 2 treatment arms, cetuximab plus chemotherapy (CTX) versus CTX alone, at a 2:1 ratio stratified by the following:

- ECOG performance status: 0 versus 1.
- Primary tumor site: oral cavity versus hypopharynx versus others.

A central stratified permuted block randomization procedure will be employed via IWRS to balance prognostic factors between treatment arms.

## 8 Overview of Planned Analyses

The main statistical analysis of data is event driven and is expected to be approximately 22 months after trial initiation (i.e., after the 144 independently-assessed PFS events with respect to the primary endpoint have occurred).

The final analysis of OS (OS cut-off date should be after at least 180 deaths [e.g., 75% of randomized subjects] have been reported, or up to 12 months after the last subject is randomized, whichever is earlier), will be presented in a clinical trial report addendum. Safety data collected after the OS cut-off will be reported using patient profiles. No additional statistical analyses will be conducted.

## 9 Changes to the Planned Analyses in the Clinical Trial Protocol

Not Applicable.

## 10 Protocol Deviations and Analysis Sets

### 10.1 Definition of Protocol Deviations and Analysis Sets

Important protocol deviations are protocol deviations that might significantly affect the completeness, accuracy, and/or reliability of the study data or that might significantly affect a subject's rights, safety, or well-being.

The following deviations will be identified and confirmed prior to or at the last Data Review Meeting.

- Important protocol deviations include
  - Deviations from the inclusion and exclusion criteria
  - Deviations post inclusion
- A subset of these important protocol deviations is defined as being clinically important if leading to the exclusion of the subject from the PP set (see section 10.2).

Details on the important protocol deviations are provided in the [Appendix 1](#).

All the important protocol deviations should be documented in CDISC datasets whether identified through site monitoring, medical review or programming. Important Protocol Deviations as well as all clinically Important Protocol Deviations will be listed.

More details about important protocol deviations identification are provided in [Appendix 1](#).

### 10.2 Definition of Analysis Sets and Subgroups

#### Screening Analysis Set

The Screening (SCR) analysis set includes all subjects who signed the informed consent.

### Intention-to-Treat Analysis Set

The intention-to-treat (ITT) analysis set includes all subjects who were randomized to trial treatment. Analyses performed on the ITT analysis set will take into account subjects' allocation to treatment groups as randomized

### Safety Analysis Set

The safety (SAF) analysis set includes all subjects who received at least one dose of any trial treatment (cetuximab, cisplatin/carboplatin, or 5-FU). Analyses performed on the safety analysis set will consider subjects as treated. As soon as a subject received at least one dose of cetuximab, treatment group corresponding to cetuximab in combination with cisplatin plus 5-FU will be considered as the treatment group for this subject. If a subject receives no dose of cetuximab, then the treatment group corresponding to cisplatin plus 5-FU alone will be considered as the treatment group for this subject.

The safety analysis set will be used for safety analyses.

### Per Protocol Analysis Set

The per protocol (PP) analysis set includes all ITT subjects who does not meet one or more of the following criteria:

- Deviations from the inclusion and exclusion criteria:
  - Inclusion criteria not fulfilled (#02): No histologically and/or cytologically confirmed diagnosis of SCCHN
  - Inclusion criteria not fulfilled (#03): No recurrent and/or metastatic SCCHN not suitable for local therapy
  - Inclusion criteria not fulfilled (#06): ECOG performance status of 0 or 1
  - Exclusion criteria fulfilled (ex#01): Prior systemic chemotherapy, except if given as part of multimodal treatment for locally advanced disease which was completed within 6 months before trial entry. (as per Protocol Amendment)
  - Exclusion criteria fulfilled (ex#03): Previous treatment with monoclonal antibody or signal transduction inhibitors targeting EGFR.
  - Exclusion criteria fulfilled (ex#04): Nasopharyngeal carcinoma.
- Randomization error:
  - Incorrect treatment group allocation, different to assignment at randomization
  - Subject randomized but did not receive any trial treatment
- Use of prohibited medication:
  - Additional concurrent chronic systemic immune treatment, chemotherapy, radiotherapy (with exceptions), hormone treatment for treatment of cancer (with exceptions), traditional Chinese medication with approval for use as anticancer treatment or any other investigational agent

- Availability of measurement of the primary endpoint:
  - No evaluable post-baseline tumor assessment (as per IRC) is available

If the Per Protocol analysis set includes at least 90% of subjects in the ITT analysis set, additional efficacy analyses on the Per Protocol analysis set and baseline analysis (including demographics) on PP/safety set will be omitted as the differences in the results based upon these two analysis sets are expected to be negligible.

| Analyses                       | Intent-to-Treat Analysis Set | Per Protocol Analysis Set | Safety Analysis Set |
|--------------------------------|------------------------------|---------------------------|---------------------|
| Demographics                   | ✓                            | ✓                         | ✓                   |
| Baseline Assessments           | ✓                            | ✓                         |                     |
| Past and Concomitant Therapies | ✓                            |                           |                     |
| Compliance and Exposure        |                              |                           | ✓                   |
| Efficacy: Primary              | ✓                            | ✓                         |                     |
| Efficacy: Secondary            | ✓                            |                           |                     |
| Safety and Tolerability        |                              |                           | ✓                   |

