Primary endpoint: The primary endpoint is PFS time, as assessed by an IRC.

Secondary endpoints: The secondary endpoints include PFS time, as assessed by the Investigator, OS time, BOR rate, DCR, duration of response, and safety.

Pharmacokinetics: Not applicable.

Other assessments: Not applicable.

Diagnosis and key inclusion and exclusion criteria:

Trial population: Subjects who have recurrent and/or metastatic SCCHN excluding nasopharyngeal carcinoma and who have not received chemotherapy for recurrent and/or metastatic SCCHN.

Key inclusion criteria:

- \geq 18 years of age.
- Histologically and/or cytologically confirmed diagnosis of SCCHN.
- Recurrent and/or metastatic SCCHN, not suitable for local-regional treatment. Subjects with recurrent disease only (no metastases) must have received prior radiotherapy (as adjuvant treatment after surgery or as treatment for locally advanced SCCHN) as part of "loco-region al treatment", and the radiotherapy must have been completed more than 6 months before screening imaging.
- Presence of at least 1 measurable lesion according to RECIST version 1.1.
- Signed written informed consent before any trial-related activities are carried out.
- ECOG performance status of 0 or 1.

Key exclusion criteria:

- Prior systemic chemotherapy, except if given as part of multimodal treatment, for locally advanced SCCHN that was completed more than 6 months before randomization.
- Major surgery or irradiation within 4 weeks before randomization.
- Previous treatment with monoclonal antibody or signal transduction inhibitors targeting epidermal growth factor receptor.
- Nasopharyngeal carcinoma.
- Known central nervous system metastasis and/or leptomeningeal disease.
- Medical or psychological condition that would not permit the subject to complete the trial or sign informed consent.
- Legal incapacity or limited legal capacity.

Investigational Medicinal Product: dose/mode of administration/ dosing schedule:

Cetuximab, supplied in ready-to-use 20 mL vials containing 5 mg/mL solution, will be administered on a weekly basis to subjects in Arm A. The initial dose will be 400 mg/m² as an intravenous infusion up to a maximum speed of 5 mg/minute. The subsequent weekly dose will be 250 mg/m² as an intravenous infusion up to a maximum speed of 10 mg/minute.

Reference therapy: dose/mode of administration/dosing schedule:

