5.3.2 Exclusion Criteria

Subjects are not eligible for this trial if they fulfill any of the following criteria:

- 1. Prior systemic chemotherapy, except if given as part of multimodal treatment for locally advanced SCCHN that was completed more than 6 months before randomization.
- 2. Major surgery or irradiation within 4 weeks before randomization.
- 3. Previous treatment with monoclonal antibody or signal transduction inhibitors targeting EGFR.
- 4. Nasopharyngeal carcinoma.
- 5. Known allergic reaction against any of the components of the trial treatment.
- 6. Active infection including active tuberculosis, known and declared human immunodeficiency virus (HIV) infection, or active hepatitis B/C virus (HBV/HCV) infection resulting in an impaired liver function or cirrhosis (see Section 7.2.4).
- 7. History of organ allograft, autologous/allogeneic stem cell transplantation, and renal replacement therapy.
- 8. Asymptomatic severe hypertension or hypertensive crisis defined as systolic blood pressure ≥180 mmHg and/or diastolic blood pressure ≥110 mmHg under resting conditions.
- 9. Impaired cardiac function, evidenced by any of the following conditions:
 - o Left ventricular ejection fraction < 45%
 - Serious arrhythmia
 - Unstable angina pectoris
 - o Congestive heart failure New York Heart Association class III or IV
 - o Myocardial infarction within the 12 months before randomization
 - o Pericardial effusion.
- 10. Known central nervous system metastasis and/or leptomeningeal disease. Subjects with neurological symptoms should undergo a CT/MRI of the brain to exclude brain metastasis.
- 11. Known uncontrolled diabetes mellitus, pulmonary fibrosis, interstitial lung diseases, acute pulmonary diseases, or liver failure.
- 12. Peripheral neuropathy or hearing loss ≥Grade 2.
- 13. Subjects not recovered from any acute effects of prior surgery, chemotherapy, or radiation therapy, that is, to \leq Grade 1 (CTCAE, version 4.03). Chronic late toxicities resulting from

prior radiation and/or surgery (pharyngeal/laryngeal toxicity, i.e., xerostomia, speech, swallowing abnormalities etc.) are permitted if nutritional status is stable.

- 14. Known alcohol and/or drug abuse.
- 15. Medical or psychological condition that would not permit the subject to complete the trial or sign informed consent.

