### 12.2.2 Reasons Leading to the Exclusion from an Analysis Set

Subjects who meet at least one criteria described in section 10.2 will be excluded from the PP. For these subjects, each criteria will be summarized and listed;

- Frequency table per criteria

Listing of each criteria.

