Appendix 1 Important Protocol Deviations

| Important Protocol Deviations   | Clinically Important PD (Y/N) | Can be programmed or not (Y/N) |
|---|-------------------------------|--------------------------------|
| Inclusion criteria not fulfilled  |                               |                                |
| Inclusion criteria not fulfilled (#02): No histologically or cytologically confirmed diagnosis of SCCHN   | Y                             | Y                              |
| Inclusion criteria not fulfilled (#03): No recurrent and/or metastatic SCCHN not suitable for local therapy   | Y                             | Y                              |
| Inclusion criteria not fulfilled (#06): ECOG performance status of 0 or 1   | Y                             | Y                              |
| Exclusion criteria fulfilled  |                               |                                |
| Exclusion criteria fulfilled (ex#01): Prior systemic chemotherapy, except if given as part of multimodal treatment for locally advanced disease that was completed within 6 months before trial entry. (Amendment)  | Y                             | Y                              |
| Exclusion criteria fulfilled (ex#03): Previous treatment with monoclonal antibody or signal transduction inhibitors targeting EGFR.   | Y                             | Y                              |
| Exclusion criteria fulfilled (ex#04): Nasopharyngeal carcinoma.   | Y                             | Y                              |
| All patients who don't fulfill other inclusion criteria or fulfill exclusion criteria.  | N                             | Y                              |
| Other Protocol Deviations   |                               |                                |
| Randomization error: Incorrect treatment group allocation, different to assignment at randomization   | Y                             | Y                              |
| Randomization error: Subject randomized but did not receive any study treatment   | Y                             | Y                              |
| Randomization error: Stratification error   | N                             | Y                              |

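### SAP 10.2 and Appendix 1 reverse the 6-month window in exclusion criterion 1, so per-protocol membership and the deviation tables would be wrong if coded as written

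*SAP*

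**What the plan says.** Protocol 5.3.2 item 1 excludes prior systemic chemotherapy, "except if given as part of multimodal treatment for locally advanced SCCHN that was completed more than 6 months before randomization". The synopsis carries the same rule: "except if given as part of multimodal treatment, for locally advanced SCCHN that was completed more than 6 months before randomization". SAP Section 6, which summarizes the trial, agrees: "for locally advanced SCCHN that was completed more than 6 months before randomization".

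The two SAP places that drive the analysis say otherwise. Under the Per Protocol Analysis Set heading, SAP 10.2 exempts chemotherapy "given as part of multimodal treatment for locally advanced disease which was completed within 6 months before trial entry. (as per Protocol Amendment". The matching row of SAP Appendix 1 reads "except if given as part of multimodal treatment for locally advanced disease that was completed within 6 months before trial entry", and is marked Y for clinically important and Y for programmable.

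SAP 12.2.2 makes the 10.2 list decisive: "Subjects who meet at least one criteria described in section 10.2 will be excluded from the PP". It also calls for a frequency table and a listing by criterion. SAP 10.1 adds a safeguard, in that "deviations will be identified and confirmed prior to or at the last Data Review Meeting". SAP Section 9, headed "Changes to the Planned Analyses in the Clinical Trial Protocol", is marked not applicable.

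**The concern.** The protocol lets in subjects whose multimodal treatment for locally advanced disease ended long enough ago, and keeps out those treated recently. The SAP sentence attaches the exemption to recent treatment. A programmer working from 10.2 or Appendix 1 would apply the opposite rule to everyone who had such treatment.

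This is not a rare history. Under protocol exclusion 1, the only prior systemic chemotherapy an eligible subject can have had is multimodal treatment completed more than 6 months before randomization. Read literally, the SAP removes every such subject from PP. The SAP clearly expects these subjects, because 10.2 also defines subgroups by prior neoadjuvant or induction therapy, prior radiochemotherapy and prior platinum.

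At stake are:

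- who is in the PP set;
- the 90% rule that decides whether the PP analysis of the primary endpoint is run (SAP 10.2, 16.1.1 and 16.1.2) and whether demographics are repeated on the PP and safety sets (SAP 13.1);
- the important-deviation and PP-exclusion tables and listings (SAP 12.2.1 and 12.2.2).

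**Working it through.** **Step 1: compare the two rules on possible histories.** No stated figure needs reproducing, because the point is the direction of a logical rule. The protocol flags a subject who had prior systemic chemotherapy unless it was multimodal for locally advanced disease and ended more than 6 months before. The SAP, read literally, flags a subject with prior systemic chemotherapy unless it was multimodal and ended within 6 months. The 9- and 3-month cases are examples.

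| Prior chemotherapy | Protocol: deviation? | SAP as written: deviation? | Agree? |
|---|---|---|---|
| None | No | No | Yes |
| Multimodal, ended 9 months before | No | Yes, removed from PP | **No** |
| Multimodal, ended 3 months before | Yes | No, kept in PP | **No** |
| Other systemic, ended 9 months before | Yes | Yes | Yes |
| Other systemic, ended 3 months before | Yes | Yes | Yes |

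Two of the five histories are misclassified, in opposite directions. With the protocol window restored, all five agree.

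**Step 2: how many wrong removals cross the 90% trigger?** The inputs are 240 planned subjects (protocol synopsis; SAP Section 6) and the SAP 10.2 rule that the PP efficacy analysis is omitted when PP is at least 90% of ITT.

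- 0.90 × 240 = 216, so up to 240 − 216 = 24 exclusions leave the analysis omitted.
- 25 exclusions give 215/240 = 89.6%, and the analysis is run. 25/240 = 10.4%.
- Protocol 8.5.2 sets the boundary slightly differently, omitting the analysis only when PP is more than 90% of ITT. Under that rule, 24 exclusions (exactly 90%) are enough.

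**Step 3: range for the unknown share.** The documents do not give the proportion of subjects with multimodal chemotherapy completed more than 6 months earlier. The shares below are assumptions, with no other PP exclusions.

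| Assumed share | Wrong removals | PP set | PP as % of ITT | PP analysis under SAP 10.2 |
|---|---|---|---|---|
| 5% | 12 | 228 | 95% | Omitted |
| 10% | 24 | 216 | 90% | Omitted (run under protocol 8.5.2) |
| 20% | 48 | 192 | 80% | Run |
| 50% | 120 | 120 | 50% | Run |

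If 10 other subjects are excluded for valid reasons (also an assumption), 25 − 10 = 15 wrong removals suffice; 15/240 = 6.25%.

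**Step 4: the anchor date.** The SAP counts back from trial entry and the protocol from randomization. The SAP does not define trial entry. Protocol 10.2 associates entry with informed consent, which can precede randomization by up to the 28-day screening period. This can matter only for subjects close to the 6-month mark and is secondary to the reversal.

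**The case against.** The strongest reply is that nobody would code the sentence literally. The entries in SAP 10.2 are labels pointing to numbered protocol criteria, followed by loose shorthand. The entry for inclusion criterion 6 shows this: its descriptive text names the acceptable ECOG values, so taken without its label it would remove everyone who satisfies the criterion. If the label governs, exclusion criterion 1 simply means protocol 5.3.2 item 1 and no error follows. This stands as a reason why the harm may not occur. It does not make the text right, since a programmable, clinically important row should not have to be decoded against another document.

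A second reply is that the sentence is a garbled description of the violation, meaning recent multimodal treatment. The grammar ties the 6 months to the exemption, and this reading would miss older chemotherapy that was not multimodal, which the protocol also excludes.

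Third, the SAP tags the entry as following a protocol amendment, and protocol 8.4 leaves PP details to the SAP, so the empty Section 9 does not by itself prove a mistake. That is fair as far as Section 9 goes. The amendment list is redacted, but the current protocol text and SAP Section 6 both say more than 6 months. The conclusion rests on that conflict.

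Finally, the consequences are contained. PP is one of several sensitivity analyses described as exploratory, wrong removals would tend to trigger an extra analysis rather than suppress one, and a large number of them would probably be noticed at the data review meeting. All of this is correct and limits the severity.

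**Conclusion.** The concern holds. SAP 10.2 and Appendix 1 state the exemption in exclusion criterion 1 the wrong way round, against the protocol and against SAP Section 6. Followed as written, the rule removes eligible subjects from PP, reports them as clinically important deviators, and keeps subjects who breached the criterion. The ITT primary analysis and the 0.77 criterion are unaffected.

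The size cannot be fixed from the documents. If 240 subjects are randomized, 25 PP exclusions in total trigger the PP analysis under the SAP rule. An affected share of 5% to 10% would not reach that alone, whereas 20% or more would. Even below the trigger, the deviation and PP-exclusion tables would be wrong. All of this is conditional on literal coding that is not caught at data review. It should be corrected because the text is the working specification and the correction is trivial.

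**What to change.** In SAP 10.2 and in the Appendix 1 row, replace the text of exclusion criterion 1 with that of protocol 5.3.2 item 1: prior systemic chemotherapy, "except if given as part of multimodal treatment for locally advanced SCCHN that was completed more than 6 months before randomization". This also brings the anchor date back to randomization. Then check the corresponding line of the deviation program specification against it before the data review meeting.

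The cost is two text edits and one specification check. No new data, analysis or eligibility rule is involved.
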